5.2 Study Procedures and Visit Descriptions

5.2.1 Prescreening, Screening and Baseline Evaluation (Pre-study)

All individuals who enter screening, as defined in this section, should be assigned a screening number and recorded on the "subject screening log" where information on the selection of potential subjects in the trial should be collected. The subject screening number should also be recorded on the subject's informed consent form. If a subject is enrolled, the study staff should record the enrollment date and assign a subject number. If a subject is not enrolled, an explanation should be recorded on the screening log. A CRF will not be completed for subjects who are not enrolled. These subjects will only be documented on the screening log and source records. It is the responsibility of the investigator to file the screening log in the investigator site file (ISF) to be readily available for on-site monitoring and/or inspection by relevant authorities. Screening may take place over more than one day and up to one month prior to Visit 1. If, after reviewing all information, the investigator concludes that a subject is eligible, he will enroll the subject in the study. Visits will be scheduled consecutively as described in the Time and Events Table.

- a. Explain and obtain written informed consent from the subject. Written informed consent must be obtained prior to performing any tests or evaluations for the study.
- b. Assign the subject a screening number. Complete the screening log.
- c. Subjects will provide a medical and psychological history.
- d. Review the ability of females of childbearing potential to become pregnant and their commitment to practice appropriate birth control as determined by the investigator for the total duration of the study.
- e. A physician will perform a general physical examination. The examination will involve the following procedures:
 - blood pressure
 - pulse
 - height
 - weight
 - body temperature

- examination of head, eyes, ears, nose, throat, skin, heart, lungs, abdomen and extremities
- brief neurological exam (cranial nerves 2-12, sensory, motor, reflexes and cerebellar function)
- electrocardiogram (ECG)
- serum electrolytes, metabolic profile, urinalysis and complete blood count
- Human Immunodeficiency Virus (HIV) serology
- Urine-dip pregnancy test on females with childbearing potential
- C-SSRS to assess suicide risk

Results of HIV serology will be kept confidential, and appropriate referral for counseling will be made if necessary. The clinical laboratory values will be used to establish eligibility and will be kept with the subject's source record. The clinical laboratory values will not be captured in the CRF, but will be used to establish eligibility and will be kept with the subject's source record. Clinically significant abnormal vales will be captured as medical history. If, upon examination, there are questions raised about possible medical problems, the therapists will request a review of subject medical records and request additional tests or assessments as indicated.

An independent rater who will not be present during any of the therapy sessions will administer:

- SCID to assess eligibility
- CAPS to assess PTSD symptoms
- PDS to assess self-reported PTSD symptoms
- BDI-II to assess depression symptoms
- GAF to assess general psychological function
- PSOI to assess sleep quality

5.2.2 Preparatory Psychotherapy Sessions (Visits 1, 2 and 3)

Subjects who do not complete all screening activities will not be enrolled. If all inclusion criteria and no exclusion criteria are met, eligibility will be confirmed with the subject during Visit 1. After eligibility is confirmed, the subject will be enrolled during Visit 1 and issued a subject number. The first preparatory session will take place after enrollment during Visit 1. Remaining preparatory sessions will be scheduled as described in the Time and Events table.

Upon enrollment, subjects who must refrain from taking a psychiatric medication will begin tapering off that medication following a time course appropriate for the medication given its half-life, with the first experimental session scheduled to occur after complete washout. The therapists will perform the C-SSRS once after medication washout but prior to the first experimental session. This may occur during a scheduled administration of the C-SSRS during the second preparatory session, or at an additional time appropriate to the medication washout.

a. Record preparatory sessions to audio and video. Subjects may receive

- copies of audio or video recordings from these preparatory sessions upon request.
- b. AEs and Medications will be recorded as described in Section 8.5 and 9.0 of the protocol from the time the subject is enrolled at Visit 1.
- c. The therapists will inquire about any possible changes in the subject's health to ensure that subject continues to meet eligibility criteria and if applicable, will confirm that the subject has appropriately tapered off of medications.
- d. The subject will undergo three preparatory sessions lasting at least an hour with the therapists, who will be a male and a female co-therapist team. The therapists will work with the subject to prepare him or her for MDMA-assisted psychotherapy. The therapists and subject will seek to form a strong working relationship with each other, and they will help the subject prepare for upcoming experimental sessions. Preparatory sessions will promote a safe space for confronting trauma-related memories, emotions and thoughts. Subjects will remain with the therapist team they begin with throughout the study.
- e. The subject and therapists will discuss goals for the experimental session and will review what will happen during the experimental session, following standard procedures and techniques discussed in the Sponsor's treatment manual.
- f. During one of the preparatory sessions the therapists will introduce the subject to the attendant that will remain with the subject during each overnight stay after each MDMA-assisted psychotherapy session. The attendant will be an individual with previous training in managing psychological distress.
- g. If a subject would like another individual present during or after the experimental session, a meeting between the therapists and that individual will be scheduled prior to the first experimental session. There must be mutual agreement between the subject and therapists concerning the presence of the support individual.
- h. Subjects will complete the C-SSRS just prior to beginning the second preparatory session, unless a subject is still undergoing medication washout. Subjects still undergoing medication washout will complete the C-SSRS during the second preparatory session or at a point after washout is complete.
- i. General wellbeing will be assessed at each preparatory session.
- j. AEs and medications will be collected as described in Sections 8.5 and 9.0 of the protocol.
- k. During the third and last preparatory session, the therapists will give the Subject Information Sheet to the subject, which includes instructions and restrictions for conduct 24 hours prior to receiving the drug, including restrictions on food and alcohol consumption. Subjects must agree to take:
 - Nothing by mouth except alcohol-free liquids after 24:00 (midnight) the evening before the experimental session.
 - Subjects must also refrain from the use of any psychoactive drug, with the exception of caffeine or nicotine, within 24 hours of each experimental session.
 - Subjects must not use caffeine or nicotine for 1 hour before and 3 hours after ingesting the drug, or until therapists deem it safe to do so.
 - Subjects must refrain from smoking marijuana for at least 3 days prior to the experimental session. They may smoke marijuana on the 8th day after the experimental session if needed. This will be collected with the Concomitant Medications.

5.2.3 Experimental Sessions (Visit 4 and 8)

Subjects in Stage 1 will receive two double-blind experimental sessions of MDMA-assisted psychotherapy scheduled approximately 3-5 weeks apart, and subjects in the open label leadin and open label Stage 2 will receive two experimental sessions with the full dose of MDMA. Procedures for MDMA-assisted psychotherapy will remain the same across all sessions, and all procedures except the drug received will be the same.

- a. At least 24 hours prior to the first experimental session the subject will be randomized. The therapist team conducting the session will obtain the container assignment using a web-based randomization program prior to the session.
- b. On the day of the experimental session, the subject will arrive approximately 1-1.5 hours prior to drug administration.
- c. Confirm continuing eligibility by reviewing inclusion/exclusion criteria.
- d. Perform a urine drug screen. A positive drug screen will be reviewed by the investigator and may be cause for delaying drug administration to a later time, rescheduling the session to a later date, or withdrawing the subject from the study.
- e. If a woman is of childbearing potential, perform a urine pregnancy test. A positive pregnancy screen is cause for withdrawal from the protocol.
- f. If the subject continues to meet criteria and the subject reports that he/she followed appropriate rules and restrictions, the session will proceed.
- g. Review procedures for the experimental session with the subject.
- h. Record the entire session to video and audio. Subjects may receive a copy of audio or video recordings of their experimental sessions upon request.
- i. The session will last for approximately eight hours or longer, followed by an overnight stay at the study site.
- j. The subject will complete the C-SSRS approximately one hour to a half hour prior to drug administration.

Table 4. Schedule of procedures and measures for experimental sessions.

Approximate Time	Procedure or Action
9:00	Urine drug screen and pregnancy test. Subject acclimated to
0.45	environment, C-SSRS
9:45	Baseline BP, Pulse, Subjective Units of Distress Rating (SUD)
9:55	2 nd Baseline BP, Pulse, Body Temperature (BT), SUD
10:00	MDMA Administration, begin recording to audio and video
10:30	BP, Pulse
11:00	BP, Pulse, SUD, BT
11:30	BP, Pulse; Can administer optional supplemental dose
12:00	BP, Pulse, BT
12:30	BP, Pulse, SUD
13:00	BP, Pulse
13:30	BP, Pulse, BT
14:00	BP, Pulse, SUD

Every hour, and as	BP, Pulse
needed	
Every 60-90 minutes	SUD, BT
Approximately 6	C-SSRS, General Wellbeing
hours after drug	
administration	

- k. Before drug administration, discuss and review the subject's goals, intentions and concerns and some of the commonly experienced effects of MDMA.
- 1. Instruct the subject not to use caffeine or nicotine 1 hour before or 3 hours after the dose of drug.
- m. Subject body temperature will be measured 15 and 5 minutes prior to initial dose administration and approximately every hour after that. The therapists may make more frequent measurements if body temperature exceeds more than 1°C above baseline.
- n. Subjects will complete the SUD 15 and 5 minutes prior to initial dose administration. Subjects will complete the SUD every 60 to 90 minutes, until the session is over, allowing a window of up to 30 minutes to fit into the psychotherapy process where a natural break occurs. If necessary, the therapists can make a greater number of measurements as their clinical judgment dictates.
- o. Measure blood pressure and pulse 15 and 5 minutes prior the experimental session, and once every half-hour throughout the experimental session if the established thresholds for normal blood pressure and pulse have not been exceeded for the duration of the experimental session. More frequent measures will be taken if the established thresholds of 160 systolic, 110 diastolic or pulse 110 are exceeded. Measurements should be taken every 5 minutes until the values fall below these levels or until they have been decreasing for 15 minutes or have stabilized at a level judged by the investigator to be safe. The therapists may also make more frequent measurements if a subject exhibits symptoms indicative of hypertension.
- p. At approximately 10:00 in the morning, subjects will receive the initial dose of drug along with a glass of water.
- q. The subject will sit or recline on comfortable furnishings. Eyeshades and a program of music will be provided if the subject wishes to use them. Subjects will listen to a program of music designed to support their experience by initially aiding relaxation and later evoking and supporting deep emotions and the emergence of unconscious material [77-79]. Subjects may speak to the therapists whenever they wish, who will provide guidance and support as needed.
- r. After the first hour, if the subject has not spoken spontaneously, check in with him/her about the nature of the experience. For the rest of the experience, as appropriate, the therapists will support and encourage the subject in emotional processing and resolution of whatever psychological material is emerging.
- s. Record any spontaneously reported reactions during the session.
- t. Provide water and electrolyte containing fluids throughout the session but not to exceed 3 L overall.

- u. A supplemental dose half the size of the initial dose may be administered approximately 1.5 to 2.5 hours after the initial dose upon mutual agreement between the therapists and subject.
- v. Provide food during the latter part of the session.
- w. If there is a support-individual who has previously been asked and has agreed to be present during part or all of the MDMA session, that person may arrive during the session at whatever time has been agreed upon, but will wait in the waiting room until brought back to the session room by one of the therapists. The support person may arrive after the session has ended.
- x. If it is appropriate to do so, initiate the first question of the C-SSRS at any point in the session if the subject is experiencing significant psychological distress that does not respond readily to processing with the therapists according to the methods described in the MDMA-assisted psychotherapy treatment manual.
- y. End the session if all medical and psychiatric parameters are acceptable and the subject is alert, ambulatory and emotionally stable.
- z. The therapists will depart the site when they have concluded that the subject is emotionally and medically stable. Therapists shall remain available to subjects during the experimental session and for one week after via 24-hour cellular phone.
- aa. Spontaneously reported reactions, AEs and Medications will be collected as described in Sections 8.5 and 9.0 of the protocol.

Subjects will remain overnight in an appropriately furnished room at the study site. With the approval of the therapists, a companion may accompany the subject during the overnight stay. An attendant will check in periodically on the subject during the overnight stay, even if a companion is present. The attendant will monitor subject health and will help subjects relax during the overnight stay. The attendant will be an individual with some previous training in managing psychological distress. If there is an emergency or the subject needs additional support, the attendant can contact the therapists. The subject and a companion (if applicable) will receive information that will allow them to contact the therapists during the overnight stay in the case of an emergency or request for additional support. Subjects will be encouraged to use much of the time during their overnight stay for rest and for a period of reflection and integration in a quiet atmosphere.

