2.3 Protocol Purpose

This Phase 2 study is a randomized, double-blind study in 10 subjects comparing the effects of low and full dose MDMA as an adjunct to manualized psychotherapy. The first two subjects will be enrolled in the open label full dose lead-in. The remaining eight subjects will enroll in Stage 1 of the protocol and receive either an active placebo dose (low dose) or a fully active dose of MDMA during two experimental psychotherapy sessions, each lasting six to eight hours and scheduled three to five weeks apart. Five subjects will be randomized to the full dose and 3 subjects will be randomized to the active placebo dose of MDMA. The extent of PTSD symptoms will be assessed at baseline, and two months after the second experimental session by a clinician and throughout using a self-report measure. Subjects enrolled in Stage 1 who receive the active placebo will have the opportunity to enroll in Stage 2 of the protocol and complete open-label experimental sessions with the fully active dose of MDMA on the same schedule as Stage 1. Participants assigned to receive the full dose of MDMA will be assessed at 12 months after the second experimental session of Stage 1, and participants assigned to active placebo who enroll in Stage 2 will be assessed 12 months after the second Stage 2 experimental session. This study will allow comparison between the impact of active placebo and full dose MDMA on PTSD symptoms, and on symptoms of depression and sleep quality. This study will also permit the refinement of the treatment manual.

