5.1.2 Safety Measures

Safety measures, vital signs and a measurement of psychological distress will be assessed during all experimental sessions. Subjects will rate their current degree of subjective distress with a single-item, self-report scale, the SUD scale, repeatedly during the experimental sessions, with the degree of distress marked along seven points.

The C-SSRS (Hebrew translation) is a clinician-administered measure of suicidal behavior devised to detect potential suicidal thoughts or behaviors during a clinical trial [92]. It consists of a "Baseline" form that assesses lifetime suicidal ideation, ideation intensity and behavior, and a form for assessing current suicidal ideation and behavior. The C-SSRS consists of a series of questions, and can be administered during a face-to-face interview or over the telephone. Suicidality will be assessed at baseline, once during any face-to-face visit, during the second and seventh days of telephone contact, and twice during each experimental session. Subjects who are discontinuing medication to participate in the study will complete the C-SSRS before and after medication washout. The C-SSRS data will be collected on Case Report Forms (CRFs) for all administrations except for the second integrative session, unless an increase in suicidality is observed by the therapists. C-SSRS data from the second integrative session after each experimental session will be kept with the subject's source record.

The therapists will assess general wellbeing during each preparatory session, on each integrative session and integrative telephone calls for seven days.

Blood pressure and heart rate will be assessed periodically during each experimental session. Blood pressure and pulse will be measured at the outset of the experimental session, and once approximately every 30 minutes during the experimental session. More frequent measures will be taken if the established thresholds of 160 systolic, 110 diastolic or pulse of 110 are exceeded. Blood pressure will also be measured more frequently if there are symptoms, such as chest pain, shortness of breath or neurological symptoms,

that may be indicative of hypertension. The therapists will measure subject body temperature approximately every 60 to 90 minutes. Cardiovascular effects will be assessed via blood pressure measurement. The timing of these measurements will be adjusted so they do not interfere with the therapeutic process.

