7.2.1 Cardiovascular and Sympathomimetic Effects

The full dose of 125 mg, followed by a supplemental dose of 62.5 mg after 1.5 to 2.5 hours, is expected to produce significant but transient, self-limited increases in blood pressure and heart rate. These changes should last no more than six hours. In less than 5% of volunteers in Phase 1 studies, increases in blood pressure were higher than 140/90 mmHg. Clinical intervention was not required in any of these cases. Nonetheless, careful monitoring of participants and predefined contingency plans will allow the researchers to rapidly identify and manage any related toxicity. For more information, see the Investigator's Brochure.

Risks posed by elevated blood pressure will be addressed by excluding people with hypertension and monitoring blood pressure and pulse as described in Safety Measures section 5.1.2. During experimental sessions the co-therapists will continually evaluate the patient for increasing blood pressure and signs or symptoms of a developing hypertensive or other cardiovascular emergency. Subjects reporting chest pain, shortness of breath or neurologicfal symptoms or other potential indicators of hypertension will have more frequent measurements. Any participant who experiences sustained blood pressure of > 220 systolic or > 120 diastolic or heart rate > 75% predicted maximum during the first experimental session will not be given a second experimental session.

In case of need, subjects will be transferred to the emergency room at Assaf Harofeh Hospital. Subjects who are transferred will be accompanied by a physician or paramedic from the ICU of Maguen David Adom. Reasons for moving a patient to an ICU would include, but not be limited to, severe headache in the setting of hypertension, angina or neurological deficits regardless of blood pressure. In the case of an emergency, intravenous anti-hypertensive agents will be available in addition to the usual resuscitation drugs and equipment. The investigator and co-therapists may, at any time, make a clinical judgment to transfer the patient to the ICU for closer monitoring and additional treatment.

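### Table 4 of the protocol drops blood pressure and pulse readings to hourly after 14:00, while sections 5.1.2 and 5.2.3(o) require half-hourly readings for the whole session

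*Protocol*

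**What the plan says.** Two places in the protocol text give the same interval for blood pressure and pulse. Section 5.1.2 asks for readings "once approximately every 30 minutes during the experimental session". Section 5.2.3, item o, asks for them "once every half-hour throughout the experimental session" as long as the thresholds have not been exceeded. Both then describe when to measure more often: above 160 systolic, 110 diastolic or a pulse of 110, or when symptoms suggest hypertension. Neither describes measuring less often.

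Table 4, which sets out the session procedures, lists blood pressure and pulse at every half-hour from 10:30 to 14:00. The next row is labelled "Every hour, and as" needed, again for blood pressure and pulse.

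Section 5.1.2 also allows some flexibility: "The timing of these measurements will be adjusted so they do not interfere with the therapeutic process". On session length, section 2.3 describes sessions "each lasting six to eight hours", while item i of 5.2.3 says "The session will last for approximately eight hours or longer". On the expected rises in blood pressure and heart rate, section 7.2.1 states "These changes should last no more than six hours".

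Body temperature is given in three places too. Item m of 5.2.3 asks for readings 15 and 5 minutes before the dose and about hourly afterwards. Section 5.1.2 gives an interval of 60 to 90 minutes. Table 4 shows one baseline reading (9:55), then 11:00, 12:00 and 13:30, then every 60 to 90 minutes.

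**The concern.** The table and the text give different schedules for the same safety procedure. A team that follows item o satisfies both. A team that works from the table, as session staff may well do, falls short of 5.1.2 and item o. Section 7.2.1 names the monitoring in 5.1.2 as one of its controls for the risk of raised blood pressure, so the shortfall is in a control the protocol relies on.

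The step-down comes 4 hours after the initial dose and 1.5 to 2.5 hours after a supplemental dose, inside the period of expected elevation. Readings every 5 minutes apply once a threshold is exceeded, but in a subject without symptoms a routine reading has to find the exceedance first.

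There are two lesser consequences. The SAP (section 9.9.4) summarises vital signs at each post-baseline timepoint and counts readings above cutoff by timepoint; late timepoints would be unevenly filled if teams followed different schedules. The SAP (section 9.3) also lists procedures not performed per protocol as a deviation category, so following the sponsor's own table could be logged as a deviation.

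**Working it through.** The plan gives no reading count to reproduce, so the check counts scheduled readings under each rule.

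**Inputs**
- Initial dose at about 10:00 (5.2.3, item p, and Table 4).
- Text rule: every 30 minutes throughout (5.1.2; item o).
- Table rule: 8 listed readings from 10:30 to 14:00, then hourly. The hourly row has no clock time; its start after 14:00 is inferred from its position.
- Session length: 6 to 8 hours (2.3), or about 8 hours or longer (item i).
- Session start: item o places the two baseline readings 15 and 5 minutes before the session, and Table 4 places them at 9:45 and 9:55. This supports counting from 10:00. Counting from the 9:00 row is shown as an alternative.

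**Blood pressure and pulse, post-dose readings in a session ending L hours after the dose**

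Text: 2 × L. Table: 8 + (L − 4).

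| Session from dose | Text | Table 4 | Shortfall |
|---|---|---|---|
| 6 h (to 16:00) | 12 | 8 + 2 = 10 | 2 |
| 7 h (to 17:00) | 14 | 8 + 3 = 11 | 3 |
| 8 h (to 18:00) | 16 | 8 + 4 = 12 | 4 |
| 9 h (to 19:00) | 18 | 8 + 5 = 13 | 5 |

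If the 6 to 8 hours run from 9:00 instead, the session ends one hour earlier on the clock: 10 v 9 (to 15:00), 12 v 10 (to 16:00) and 14 v 11 (to 17:00), a shortfall of 1 to 3.

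**Position in the window of expected elevation**
- Six hours from the 10:00 dose ends at 16:00. The half-hourly times between 14:00 and 16:00 that the table leaves out are 14:30 and 15:30, so 2 readings.
- Supplemental dose: 10:00 plus 1.5 to 2.5 hours is 11:30 to 12:30. From there to 14:00 is 2.5 to 1.5 hours.
- Longest scheduled gap: 60 minutes (table) v 30 minutes (text).

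**Body temperature**
- Baseline: 2 readings in item m v 1 in Table 4, which has none in its 9:45 row.
- Item m, hourly from 11:00: 6 readings to 16:00 and 8 to 18:00.
- Table 4: 3 readings to 13:30. Continuing every 60 minutes (14:30, 15:30, 16:30, 17:30) gives 5 to 16:00 and 7 to 18:00. Continuing every 90 minutes (15:00, 16:30, 18:00) gives 4 and 6.
- The 12:00 to 13:30 gap is 90 minutes. That agrees with 5.1.2 but not with item m.

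**The case against.** The strongest reply is that this is an editorial mismatch which forces no breach. Item o stands in the same section as the table, and half-hourly readings satisfy both. Table 4 is itself protocol text and its times are headed as approximate. Section 5.1.2 lets readings move to suit the therapy. Half-hourly readings already cover the first four hours, and section 2.4 expects the supplemental dose to produce no physiological effect beyond the peak that follows the initial dose. Other safeguards remain: hypertension is an exclusion, "the co-therapists will continually evaluate the patient for increasing blood pressure and signs or symptoms" of a cardiovascular emergency, and under item y the session ends only when medical parameters are acceptable. For the analysis, section 12.0 works from baseline and post-drug peak values, the SAP output is descriptive, and both dose groups follow the same schedule.

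Most of this stands, and it keeps the point minor. It does not reconcile the text with the table. Moving a reading to suit therapy is different from scheduling half as many, and the table's as-needed wording permits extra readings without requiring them. An expectation that the later peak will be no higher does not explain why the interval should lengthen while pressure may still be raised. No bias between dose groups is shown, and none is claimed.

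Temperature is a weaker case. Table 4's post-dose times agree with 5.1.2 and conflict only with item m; the missing first baseline reading is also a conflict with item m.

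**Conclusion.** The inconsistency is real. For a session of 6 to 8 hours from the dose, Table 4 schedules 2 to 4 fewer blood pressure and pulse readings than the text requires. The shortfall is 4 or more if sessions run eight hours or longer, and 1 to 3 if 6 to 8 hours is counted from 9:00. Any session lasting at least six hours from the dose loses the 14:30 and 15:30 readings inside the expected window. The counts rest on a 10:00 dose, on the hourly row starting after 14:00, and on the stated session lengths.

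The practical effect is limited to later detection of a silent late rise and thinner late timepoints in descriptive safety tables. It is a consistency and safety correction worth making, with no bearing on the CAPS result.

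**What to change.** **Blood pressure and pulse.** Change the last row of Table 4 to every 30 minutes until the end of the session, and as needed. This keeps the interval the sponsor wrote twice. If the hourly step-down is intended, state it with its reason in both 5.1.2 and item o instead.

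**Temperature.** Add a reading to the 9:45 row of Table 4. Then use one post-dose interval throughout:
- 60 to 90 minutes needs a single edit, to item m.
- Hourly needs edits to 5.1.2 and to Table 4: readings at 13:00 and 14:00, the 13:30 reading no longer needed, and the last temperature row split because it is shared with the distress rating, which item n keeps at 60 to 90 minutes.

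**Cost.** Wording changes in one protocol amendment. Relative to Table 4, each session of 6 to 8 hours from the dose gains 2 to 4 blood pressure and pulse readings (more if longer) and one baseline temperature, plus 1 to 2 post-dose temperatures if hourly is chosen. Therapy late in the session is interrupted slightly more often.
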